2. TRIAL DESIGN

Open label randomised controlled trial, with internal pilot.

2.1 **OBJECTIVES**

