4. DATA COLLECTION & DATA ENTRY

4.1 **PARTICIPANT TIMELINE**

TABLE 1 SCHEDULE OF EVENTS

Timepoint	Screening	Baseline (-3 to 0 days)*	Day 30 +/- 3	Day 90 +/- 3	Day 180 +/- 7	1 year +/- 7	Ongoing
Registration form & consent	X						
2. Eligibility	X						
3. Medical history	X						
4. COPD history	X						
5. Demographic data	X						
Collation of routine investigations and and data on this admission eg LOS		X					
Clinical Frailty Scale		X					
The modified MRC Scale		X		X	X	X	
Dyspnea VAS		X		X	X	X	
6. Randomisation		X					
7. Status form to include VITAL STATUS, READMISSIONS and COMMUNITY TREATED EXACS			X	X	X	X	
8. Study Follow-Up Telephone call			X	X	X	X	
9. EQ-5D-5L		X		X	X	X	
10. COPD Assessment Test (CAT)		X		X	X	X	
11. Resource use questionnaire		X		X	X	X	
12. Text messaging/tel call [¥]			X	X			
13. Seriousadverse events log							X
14. Concomitant medications log		X					
15. Withdrawal form							X
16. Rescue packs dispensing		X					X †
17. Interview [¶] §				X*			
18. Biological sample collection (including stool, nasosorption, sputum)§		X		X			

^{*}in relation to discharge from hospital; *twice-weekly for 90 days in the intervention arm; *window for interviews +/- 14 days; § substudy; †resupply of rescue pack(s) if used within 90 day window.

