4.5.3 WITHDRAWAL

A withdrawal form must be completed in the event of participant death or where the participant has stopped taking study medication and is no longer prepared to provide any follow up data or have their caregiver or family doctor provide any follow up data. Where the participant has stopped study intervention but is still being followed for primary outcome data, a withdrawal form should not be completed, but a status update must be recorded in the eCRF every 3 months.

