13. STATISTICAL METHODS

13.1 **PRIMARY OUTCOME**

1. Time to first all-cause readmission within 90 days of discharge from hospital. The day of discharge will be the 1st day in the countdown to 90-day timepoint

13.2 **SECONDARY OUTCOMES**

- Time to and frequency of COPD-related readmissions at 30 and 90 days
- Days alive and out of hospital at day 90
- Time to and frequency of all COPD exacerbations at days 30 and 90
- Cumulative systemic oral corticosteroids use over 90 days, measured as proportion of period used and number of occasions used
- Cumulative systemic antibiotic use over 90 days, measured as proportion of period used and number of occasions used
- Health care contacts at baseline, days 90 and 180, and 1 year
- All cause readmission at 30 days

- All cause-, cardiovascular- and COPD- related mortality at day 90 and over 12 months
- Quality of life (COPD assessment Test (CAT) score and EQ-5D-5L) at baseline, days 90 and 180, and 1
 year
- Incremental cost-effectiveness ratio (ICER, a ratio of the additional cost divided by the additional effectiveness of SRP compared to UC) at days 90 and 180 and 1 year
- Qualitative description of usual care
- Qualitative examination of fidelity to and adaptation of the plan in the intervention arm
- Serious adverse events
- Antimicrobial resistance

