13.4 STATISTICAL METHODS FOR PRIMARY AND SECONDARY OUTCOMES

13.4.1 STATISTICAL METHODS FOR PRIMARY OUTCOME

The log-rank test will be used to test the null hypothesis of no difference in readmission-free survival distributions between arms at the two-sided 5% significance level. These data will be collected primarily from HES. If HES data is not available, then other sources of data will be used (patient-reported data, SAE forms). These distributions will be described using the Kaplan-Meier plot. The univariate Cox proportional hazards model will be used to estimate the unadjusted hazard ratio with 95% confidence interval. In our previous meta-analysis, comorbidities, previous exacerbations and hospitalisation, and increased length of stay were significant risk factors for 30-day and 90-day all-cause readmission after an index hospitalisation with an exacerbation of COPD. Chance confounding effects are not expected given the planned size of the trial and the number of events. We will however secondarily adjust for the randomisation stratifiers as main effects within the Cox model framework. This model will be extended to explore the consistency of the primary outcome result across categories of the randomisation stratifiers, and other subgroup variables defined in the statistical analysis plan. This will involve including the interaction of a subgroup variable with study arm, Randomised controlled intervention effects within subgroup categories will be estimated with 95% confidence intervals.

We will seek to idenstify an appropriate survival distribution, in order to favilitate the development of predicted probabilities of readmission and to estimate key readmission duration quantiless. The proportionality of hazards assumption will be assessed using recommended methods²⁶. The noninformative censoring assumption will be assessed in a sensitivity analysis, where the censoring of the 90-day all-cause first readmission, by a COPD-related death, is dealt with as a composite outcome. Departures from assumptions, and consequently required analysis methods will be desribed in the statistical analysis plan.

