Survival analysis methods will be used for the outcome of the number of days alive and out of hospital at day 90I, which may be censored, and for other time-to-event secondary outcomes. Strategies to minimise missing data include obtaining primary outcome dates from more than one source, capturing this in those who move outside the study area, and our PPI group having assessed questionnaire burden. Study dropout, and loss of events, are expected to be at most 5%.

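### The only stated check on censoring by death counts COPD-related deaths alone, although the primary outcome is readmission from any cause

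*Protocol*

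**What the plan says.** Protocol section 13.1 defines the primary outcome as "Time to first all-cause readmission within 90 days of discharge from hospital". Section 13.3 powers the trial on 515 first readmission events. Neither section makes death an event.

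Section 13.4.1 uses a log-rank test, a Kaplan-Meier plot and Cox models. It offers one assessment of non-informative censoring: a sensitivity analysis "where the censoring of the 90-day all-cause first readmission, by a COPD-related death, is dealt with as a composite outcome". It states no composite with death from any cause and no competing-risk analysis for the primary outcome.

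The same section words the null hypothesis as "no difference in readmission-free survival distributions between arms".

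Deaths of all causes appear elsewhere. Section 13.2 lists "All cause-, cardiovascular- and COPD- related mortality at day 90 and over 12 months" as a secondary outcome. Days alive and out of hospital at day 90 is another, for which section 13.4.1 says "Survival analysis methods will be used for the outcome of the number of days alive and out of hospital".

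**The concern.** The endpoint takes readmissions from any cause, but the death component of its check is restricted to one cause. A death from cardiovascular disease or anything else before readmission removes the patient from risk just as completely as a COPD death. The check should show whether the readmission result depends on treating deaths as uninformative. If such deaths differ between arms, it will show only the part attributed to COPD.

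The restriction also makes the check depend on attributing cause of death, in a trial described as "Open label randomised controlled trial, with internal pilot". A composite that counts every death needs no attribution.

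The null hypothesis adds an ambiguity. Readmission-free survival normally counts death as an event. If deaths were already events, a composite adding COPD deaths would be redundant. The phrase and the censoring of deaths describe two different quantities.

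**Working it through.** **1. Are deaths primary events?** Reproduce section 13.3 from the readmission rates alone (43% and 34.4%, two-sided 5%, 90% power, 1:1):

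- HR = ln(1 − 0.344) / ln(1 − 0.43) = 0.750.
- Events (Freedman) = (1.960 + 1.282)² × [(1 + 0.75)/(1 − 0.75)]² = 515, as stated.
- N = 515 / [(0.43 + 0.344)/2] = 515 / 0.387 = 1330.7, so 1331, as stated.

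The plan's figures come from readmissions only, so deaths are not counted as primary events.

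**2. What happens to each kind of death before readmission?**

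| Stated analysis | COPD-related death | Other death |
|---|---|---|
| Log-rank, Kaplan-Meier, Cox (13.4.1) | censored | censored (by implication) |
| Sensitivity composite (13.4.1) | event | censored (by implication) |

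**3. Model for the size.** The protocol gives no death rate, so every death figure below is an assumption. Let r be the proportion readmitted (0.43 control, 0.344 intervention), d the proportion dead without readmission, and s the COPD-related share of those deaths. Assume constant, proportional cause-specific hazards over 90 days:

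- total hazard = −ln(1 − r − d), split between readmission and death in the ratio r : d;
- primary HR = ratio of readmission hazards;
- planned composite HR = ratio of (readmission + s × death) hazards;
- all-death composite HR = ratio of total hazards;
- power = Φ(√events/2 × |ln HR| − 1.96), with events = 1331/2 × the sum of r + d over the two arms.

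**4. Balanced deaths: what does the wider check cost?**

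| d in both arms | All-death HR | Events | Power |
|---|---|---|---|
| 2% | 0.757 | 542 | 0.900 |
| 3% | 0.760 | 555 | 0.898 |
| 5% | 0.766 | 582 | 0.895 |
| 8% | 0.773 | 622 | 0.893 |

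**5. Unbalanced deaths: 3% control, 5% intervention.**

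- Control: total hazard −ln(0.54) = 0.616; readmission 0.576, death 0.040.
- Intervention: total hazard −ln(0.606) = 0.501; readmission 0.437, death 0.064.
- Primary HR = 0.437/0.576 = 0.759. All-death HR = 0.501/0.616 = 0.813, with 568 events and an approximate 95% CI of 0.69 to 0.96.
- Share of the shift shown = ln(planned HR / 0.759) / ln(0.813 / 0.759).

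| COPD share s | Planned composite HR | Share of shift shown |
|---|---|---|
| 0.3 | 0.776 | 32% |
| 0.5 | 0.787 | 53% |
| 0.7 | 0.798 | 72% |

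The planned composite HR at s = 0.3 depends a little on method. Converting incidences directly, without taking non-COPD deaths out of the risk set, gives ln(1 − 0.359)/ln(1 − 0.439) = 0.769.

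With 3% and 4% dead and s = 0.3, the three HRs are 0.754, 0.764 and 0.786.

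**6. How many deaths stay censored in the planned check?** 1331 × d × (1 − s) runs from 1331 × 0.02 × 0.3 = 8 to 1331 × 0.08 × 0.7 = 75. If d is no more than 5%, the upper figure is 1331 × 0.05 × 0.7 = 47.

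**The case against.** - **The protocol never says that non-COPD deaths are censored.** True; it follows by inference. Such a death is not a readmission and is outside the only composite, so no stated analysis makes it an event.
- **The size mostly restates an assumption.** Largely fair. The share of the shift shown tracks the assumed COPD share closely, and no document figure supports any particular share. All three values are therefore shown together.
- **The upper death rates may be too high.** Section 3.2.2 excludes patients with expected survival under 90 days, those needing invasive ventilation, and those discharged to residential or nursing homes. Only deaths before any readmission matter here. The 8% figure is the end of an illustrative range, not a forecast.
- **Deaths are examined elsewhere.** All-cause mortality and days alive and out of hospital would reveal an imbalance. They are separate secondary outcomes, however, and do not show whether the primary readmission result depends on censoring deaths.
- **The SAP can deal with it.** Section 13.4.1 leaves departures from assumptions, and the methods they require, to the SAP, and nothing forbids further sensitivity analyses there. But the restriction to COPD-related death is written into the protocol, so this is a stated choice and not an omission.
- **Arm-dependent attribution of cause of death is speculative, and readmission-free survival is loose wording.** Both are secondary. No size can be put on the first, and the second is an editorial companion change.

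**Conclusion.** The concern holds. An all-cause readmission endpoint is paired with a censoring check that sees only one cause of death. By implication, all other deaths before readmission are censored in every primary-outcome analysis the protocol states.

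The textual mismatch is certain; its numerical effect is not. With balanced deaths it hardly matters. With an assumed excess in the intervention arm (3% against 5%), the planned check would show between about a third and about seven tenths of the shift, depending on the COPD share. The all-death interval would still exclude 1 at the expected values. These figures rest on assumed death rates, constant proportional cause-specific hazards, and the protocol's 43% and 34.4% readmission rates.

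The log-rank test remains valid for the cause-specific readmission hazard, and the sample size is unaffected. This should be fixed because the improvement is nearly free, not because the primary result is in danger.

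**What to change.** Keep the log-rank test with deaths censored as the primary analysis, and change two phrases in section 13.4.1:

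1. Define the sensitivity composite as first readmission or death from any cause within 90 days. The version with COPD-related death may stay as an addition.
2. Reword the null hypothesis as no difference between arms in time to first all-cause readmission (cause-specific hazard, deaths censored).

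Optionally, the SAP could add the cumulative incidence of readmission with death as a competing event.

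No new data are needed. Table 1 in section 4.1 schedules a "Status form to include VITAL STATUS, READMISSIONS and COMMUNITY TREATED EXACS" at days 30 and 90. Section 4.5.3 states that "A withdrawal form must be completed in the event of participant death". Section 11 makes death a reportable serious adverse event. The primary test and sample size do not change. Making the edit before results are known avoids a later choice of which deaths count.

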13.4.2 STATISTICAL METHODS FOR SECONDARY OUTCOMES

13.4.2.1 CONTINUOUS OUTCOMES

In secondary continuous outcome analyses, each randomisation stratifier and the baseline of the outcome, will be analysed as a main effect covariate and, if necessary, using the missing indicator method. Each repeated-measures continuous outcome timepoint will be analysed using linear mixed effects models with unstructured correlation structure and with covariates, including arm, interacted with time. This beneficially includes partial responses of the outcome over time because the estimated correlations between the repeated measures act equivalently to impute missing responses applying a "missing at random" assumption given the data included in the model. As nonresponse could instead be "not missing at random", the impact of this assumption will be investigated according to available collected reasons for withdrawal and missing responses, by means of sensitivity analysis in all randomised participants across a realistic range of values for the intervention effect amongst non-responders. Details of these, and any sensitivity analyses, will be described in the approved statistical analysis plan.

13.4.2.2 BINARY OUTCOMES

Distinct from time-to-event outcomes, binary outcomes will be analysed between groups primarily as a difference in proportions. Methods for obtaining 95% confidence intervals will be reported in the statistical analysis plan.

13.5 INTERIM ANALYSES (STATISTICAL)

No formal interim analysis is planned. An internal pilot phase will assess trial parameters but not the betweenarm effectiveness measures. The DMC will provide advice to the TSC, who will advise the Sponsor in making the final decision on continuing or stopping the trial.

13.6 METHODS FOR PRE-SPECIFIED SUBGROUP ANALYSES

Below are details of two pre-specified sub-group variables:

- i) Prior versus no prior severe exacerbations in the last year (excluding the index exacerbation)
- ii) >=2 or <2 moderate/severe exacerbations in the last year (excluding the index exacerbation)

The hypothesis is that the first category of each of these subgroup variables is related to worse outcomes, more precisely a higher rate of hospital re-admission. The subgroup analysis will investigate the consistency of the randomised intervention effect on the primary outcome analysis across these subgroup categories.

13.7 METHODS TO HANDLE MISSING DATA

Our primary outcome (re-admission within 90 days of discharge from hospital) will be collected from source documentation of SAEs and HES Linkage data which is a robust method of data collection. Missing data from HES Linkage may arise from participants that have not consented for HES linkage to occur. Our experience is that this will be minimal, but to manage this, we will also collect directly from patients this information at 30 and 90 days, using pre-specified questionnaires completed by the local site or central study coordinator at the lead site and SAE forms. For the majority of our secondary outcomes, we will be using HES linkage data, which will minimise missing data. Data will be linked via a third party using NHS number. No NHS numbers will leave the NHS, instead unique study IDs will be used and data will be stored in the Safe Haven at King's College London. Named researchers will have virtual desktop infrastructure (VDI) access to log in and analyse the data as appropriate. For other secondary outcomes, including Health Economic analysis we will be using questionnaires collected over 4 timepoints. For missing EQ-5D index values at baseline, we will use mean imputation to fill in each missing index value independent of the treatment arm. We will follow the same approach for the total and different categories of costs at baseline. For missing EQ-5D index values at all follow up points, we will assume that the data are missing at random (MAR). We will replace the missing observations with a set of imputed values through multiple imputations drawn from posterior predictive distribution given the missing observed data31. For missing cost data at all follow up points, we will impute at the costs level using the same approach outlined for dealing with missing EQ-5D index values at follow up. We have limited questionnaires to the EQ-5D-5L and resource use questionnaire and the COPD assessment tool. These have been selected and prioritised to reduce burden of questionnaires to manage missing data. We have discussed this questionnaire limits with PPI and this was agreed that this design would reduce missing data, whilst not being overburdensome to patients and their carers.

13.8 PLANS TO GIVE ACCESS TO THE FULL PROTOCOL AND PARTICIPANT LEVEL-DATA

It is anticipated the full protocol and all results will be available as open access according to the rules of the funding bodies.

13.9 HEALTH ECONOMIC ANALYSIS

A cost-utility analysis will be conducted to compare the cost-effectiveness of the self-supported rescue pack intervention at day 90, 180 and one-year. In line with the recommendation of National Institute for Health and Care Excellence (NICE), a healthcare and societal costing perspective will be adopted³⁴. The primary outcome of the economic analysis will be total cost per patient, total quality-adjusted life-years (QALYs) per patient, and incremental cost-effectiveness ratio (ICER). Interventions with an ICER less than £20,000-30,000 per QALY are considered cost effective.

Data collection: Patients' use of secondary healthcare services will be collected from the trial and the HES database. Patients' use of primary healthcare services, social care services, their productivity losses and their carers' productivity losses will be collected using a resource use questionnaire adapted from a previous UK RCT³⁵ for patients with COPD at baseline, days 90, 180 and 1 year. For all health and social care services, nationally applicable unit costs will be taken from the annual Personal Social Services Research Unit (PSSRU) compendium. National Health Service reference costs and national tariffs will be used to estimate the cost of inpatient, accident and emergency and day hospital attendances where necessary. Cost of steroid medicines, antipsychotic medications and other drugs will be calculated using daily dose information and the cost of the generic drugs as listed in the British National Formulary (BNF). EQ-5D-5L³⁶, a validated and widely used generic measure will be used to collect patients' health-related quality of life data. Both the EQ-5D-5L and resource use questionnaire will be administered at baseline, days 90, 180 and 1 year.

Missing data: For missing EQ-5D index values at baseline, we will use mean imputation to fill in each missing index value independent of the treatment arm³⁷. We will follow the same approach for the total and different categories of costs at baseline. For missing EQ-5D index values at all follow up points, we will assume that the data are missing at random (MAR). We will replace the missing observations with a set of imputed values through multiple imputations drawn from posterior predictive distribution given the missing observed data³⁸. For missing cost data at all follow up points, we will impute at the costs level using the same approach outlined for dealing with missing EQ-5D index values at follow up.

Analysis: The utility scores derived from EQ-5D will be used to calculate QALY accrued over the follow-up period using area-under-the-curve methods and assuming a linear change between any two adjacent time points. Costs will be calculated using data on the type, number and length of contacts received by each participant. No discounting is needed as the maximum time horizon of the economic analysis is one year. Uncertainty of the results will be quantified by bootstrapping and reported as the cost-effectiveness planes and cost-effectiveness acceptability curve (CEAC)³⁹. Cost-effectiveness planes plot the adjusted mean differences in total cost and QALYs based on the bootstrapped results. The CEAC curve will be derived by calculating the proportion of bootstrapped estimates that are cost-effective across a range of willingness-to-pay thresholds, to show the probability that the intervention is cost-effective across different threshold values. A Health Economic Analysis Plan (HEAP) will be developed which will describe their plans in more detail.

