Why is this research important in terms of improving the health of patients and health and care services?

Reducing re-admission through provision of supported rescue pack use would benefit people living with COPD and the NHS. A reduction in readmissions of 20% could save the NHS £86 million per quarter (£344 million per annum). Conversely, demonstrating that rescue packs are not effective when used in this way will address controversy about use, and reduce pressure on antimicrobial resistance and harm from over-use of oral corticosteroids. Integrated care systems are rapidly developing out-of-hospital support for people with exacerbations of COPD including digitally supported virtual wards. The proposed trial will define the role of supported rescue pack provision in the design and implementation of these programmes, enhancing their ability to reduce demands on urgent and acute care. Whether positive or negative, this trial will help to reduce the current variation in service provision by providing a definitive answer to the study question. Furthermore, preventing exacerbations of COPD have been identified as a priority by the James Lind Alliance (JLA) Priority Setting Partnership (PSP)¹².

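### Section 13.9's unconditional ICER threshold reverses the cost-effectiveness verdict whenever incremental QALYs are negative

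*Protocol*

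**What the plan says.** Section 13.2 of the protocol lists the ICER among the secondary outcomes and defines it as "a ratio of the additional cost divided by the additional effectiveness of SRP compared to UC". Section 13.9 makes it a primary economic outcome, beside total cost and total QALYs per patient, at day 90, day 180 and one year. The same section gives the rule for reading it: "Interventions with an ICER less than £20,000-30,000 per QALY are considered cost effective".

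The analysis part of section 13.9 adds bootstrapping, cost-effectiveness planes and an acceptability curve. The curve is to be derived by "calculating the proportion of bootstrapped estimates that are cost-effective across a range of willingness-to-pay thresholds"; what makes a single draw cost-effective is not defined. Section 13.9 does not limit the rule to positive incremental QALYs. It mentions neither dominance nor net benefit, and has no separate reading for results that are cheaper but less effective. Further detail is left to a Health Economic Analysis Plan (HEAP).

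**The concern.** An ICER can be compared with a threshold from below only when the QALY difference is positive. If the intervention saves money and loses QALYs, the ICER is the saving per QALY given up, and a small value counts against the intervention. If it costs more and loses QALYs, the ICER is negative and so below any positive threshold, although the intervention is worse on both counts. A negative ICER also arises when the intervention is better on both counts, so the ratio alone cannot separate the best case from the worst.

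Followed as written, the rule can declare a dominated or poor-value intervention cost effective, and can reject one whose saving more than offsets a small QALY loss. The economic conclusion is at stake, at each of three time points.

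**Working it through.** **The plan's own figures.** Section 13.9 contains a threshold but no computed figure. The number analysed, needed below, comes from section 13.3 and reproduces. HR = ln(1 - 0.344)/ln(1 - 0.43) = 0.750. Freedman's formula with 90% power and two-sided 5% gives 515 events. The mean event rate is (0.43 + 0.344)/2 = 0.387, and 515/0.387 = 1330.7, or 1331 analysed, about 665.5 per arm.

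**The algebra.** Let dC and dQ be the cost and QALY differences (intervention minus usual care) and L the threshold. The intervention is worth its cost when net monetary benefit, NMB = L × dQ - dC, is above zero, that is, when dC < L × dQ.

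- If dQ > 0, dividing by dQ gives dC/dQ < L, which is the protocol's rule.
- If dQ < 0, dividing by dQ reverses the sign and gives dC/dQ > L, which is the opposite of the protocol's rule.

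A simulation of 2 million points per threshold (£20,000 and £30,000) agrees: the rule and NMB disagreed in 0% of points with dQ > 0 and in 100% of points with dQ < 0, whatever the sign of dC.

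**Illustrative results** (values chosen to show each case):

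| dQ | dC | ICER | Rule in 13.9 | NMB at £20,000 | NMB at £30,000 |
|---|---|---|---|---|---|
| +0.005 | +£60 | £12,000 | cost effective | +£40 | +£90 |
| +0.005 | -£300 | -£60,000 | cost effective | +£400 | +£450 |
| -0.02 | -£300 | £15,000 | cost effective | -£100 | -£300 |
| -0.005 | -£300 | £60,000 | not cost effective | +£200 | +£150 |
| -0.01 | +£200 | -£20,000 | cost effective | -£400 | -£500 |

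For the third row, NMB = 20,000 × (-0.02) + 300 = -£100. For the last, NMB = 20,000 × (-0.01) - 200 = -£400. The rule is right in the first two rows and wrong in the last three.

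**How often the QALY estimate could be negative.** The protocol gives neither a QALY SD nor an expected difference, so both are assumed. SE = SD × sqrt(2/665.5), which is 0.0082 for SD 0.15 and 0.0165 for SD 0.30. P(estimate < 0) = Φ(-true dQ/SE).

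| True one-year dQ (assumed) | P(estimate < 0), SD 0.15 to 0.30 |
|---|---|
| 0 | 50% |
| 0.005 | 27-38% |
| 0.01 | 11-27% |
| 0.02 | 1-11% |
| 0.03 | 0-3% |

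At day 90, with assumed SDs of 0.04-0.075, the chances are 50% at zero, 32-40% at 0.001, 13-27% at 0.0025 and 1-11% at 0.005.

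**The acceptability curve, if the rule were applied to each draw.** Assume dQ 0.005, QALY SD 0.2, cost SD £4,000 and independent costs and QALYs. With dC -£300, the rule gives 75% cost effective at £20,000 against 90% by NMB. With dC zero, it gives 77% against 63%. The error can go either way.

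**The case against.** The sentence can be read as a familiar threshold convention and not as an algorithm. Total cost and total QALYs are reported beside the ICER, and the planes show the quadrant, so an analyst would have to follow the sentence mechanically and ignore those outputs. Handling of dominance is ordinary content for the HEAP. These points limit the practical risk, and they stand to that extent. They do not remove the error: the rule is stated in section 13.9 without a qualifier, and the HEAP is announced as adding detail, not as replacing it.

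A reader might also infer more than the documents support:

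- *That a negative QALY estimate is likely, or that the trial expects small QALY differences.* No section gives an expected difference or an SD. The chance does not exceed 50% for a true difference of zero or more, and is only 0-3% for a one-year gain of 0.03. The bootstrap is planned on adjusted differences, whose SE may be smaller than the unadjusted one used here.
- *That expected savings point to the problem.* Section 1.1 says "A reduction in readmissions of 20% could save the NHS £86 million per quarter", which is conditional on the effect. Savings together with QALY gains fall where the rule works; only a negative QALY difference breaks it.
- *That the acceptability curve will be wrong.* The criterion per draw is undefined, and a curve built on net benefit would be correct.
- *That the £20,000-30,000 range leaves the result undecided.* The curve covers a range of thresholds, and reporting at both ends settles it.
- *That the ICER should be withheld outside the costlier, more effective quadrant.* It is a listed secondary outcome and can be reported with its quadrant.

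**Conclusion.** The point holds as a wrong-as-written rule of minor weight. The reversal for negative incremental QALYs is exact, applies at any positive threshold and rests on no assumption. How often it would matter does rest on assumptions: normal sampling error, about 1331 analysed, and QALY SDs and true differences that the protocol does not give. Over the ranges shown, the chance of a negative one-year estimate runs from 50% (no true difference) down to 0-3% (true gain of 0.03), so such a result is plausible but not shown to be likely. An error in the acceptability curve is conditional on the rule being applied draw by draw. Only the economic conclusion is affected; the primary clinical analysis and the sample size are not.

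**What to change.** In section 13.9, and carried into the HEAP:

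- Base the cost-effectiveness conclusion on incremental net monetary benefit above zero, at £20,000 and at £30,000 per QALY, each with a 95% confidence interval.
- Define a bootstrap draw as cost-effective at a given threshold when its net monetary benefit at that threshold is above zero, and build the acceptability curve on that.
- Keep reporting the ICER at all three time points with its quadrant. State dominance (in either direction) where costs and QALYs favour the same arm, and label the ratio as saving per QALY forgone where both are lower.

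This takes one or two sentences and uses the bootstrap output already planned. It needs no new data and no change to the sample size.
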